	Suppl. estimand for binary endpoints	Treatment-policy: 
 
- Permanent discontinuation of IMP.
 
- Initiation of rescue treatment.
 
	Subjects with moderate-to-severe AD.		
To compare the safety of 4 different dose regimens of LEO 138559 with placebo in subjects with moderate-to-severe AD.	Primary estimand for time-to-event endpoints	While on treatment: 
 
- Permanent discontinuation of IMP.
 
	Subjects with moderate-to-severe AD.	Difference in the cumulative incidence at Week 16.	Exploratory endpoint: 
 
• Time from baseline to use of any rescue treatment.
 

	Suppl. estimand for time-to-event endpoints	Composite: 
 
- Permanent discontinuation of IMP.
 
	Subjects with moderate-to-severe AD.	Difference in the cumulative incidence at Week 16.	Exploratory endpoint: 
 
• Time from baseline to use of any rescue treatment.
 

**Abbreviations:** AD = atopic dermatitis; AE = adverse events; ADSD = Atopic Dermatitis Symptom Diary; DLQI = Dermatology Life Quality Index; EASI = Eczema Area and Severity Index; EASI-50 = at least 50% decrease in EASI score; EASI-75 = at least 75% decrease in EASI score; EASI-90 = at least 90% decrease in EASI score; EASI-100 = at least 100% decrease in EASI score; EQ-5D-5L = EuroQoL 5 Dimension Health Questionnaire 5 Level; HADS = Hospital Anxiety and Depression Scale; IMP = investigational medicinal product; POEM = Patient-Oriented Eczema Measure; Suppl. = supplementary; VAS = Visual Analogue Scale; vIGA-AD = Validated Investigator Global Assessment Scale for Atopic Dermatitis; WPAI-SHP = Work Productivity and Activity Impairment: Specific Health Problem.

THIS DOCUMENT CONTAINS CONFIDENTIAL INFORMATION AND MUST NOT BE COPIED OR MADE AVAILABLE TO ANY THIRD PARTY WITHOUT THE PRIOR WRITTEN CONSENT OF THE LEO PHARMA GROUP

TMF-000757181 - Version 5.0

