### Description of intercurrent events

An intercurrent event refers to a post-baseline event that affects either the interpretation or the existence of the measurements of an endpoint. For the purposes of this trial, we define the following 2 intercurrent events:

- ***Initiation of rescue treatment:*** This event occurs when a subject initiates rescue treatment as listed in no. 1-6 of Section 6.7 for intolerable AD signs and/or symptoms. The timing of the event will be taken as the date of initiation of the rescue treatment recorded in the eCRF.
- ***Permanent discontinuation of IMP:*** This event occurs when a subject permanently discontinues IMP. This event can occur either at the subject's own initiative or at the investigator's or sponsor's discretion. The timing of the event will be taken as the date of permanent discontinuation of IMP as recorded in the eCRF.

[Panel 16](#) provides an overview of the estimand strategies defined in Sections 11.3.7.1, 11.3.7.2, and 11.3.7.3 that will be used to address occurrences of the intercurrent events described above.

An overview of statistical analysis of endpoints can be found in [Panel 17](#).

THIS DOCUMENT CONTAINS CONFIDENTIAL INFORMATION AND MUST NOT BE COPIED OR MADE AVAILABLE TO ANY THIRD PARTY WITHOUT THE PRIOR WRITTEN CONSENT OF THE LEO PHARMA GROUP

**Panel 16: Handling of observed and missing data according to intercurrent events in the primary analysis of the estimands defined in Sections 11.3.7.1, 11.3.7.2, and 11.3.7.3**

Events	Observed data or missing	Continuous endpoints			Binary endpoints		TTE endpoints
		Primary Estimand	Hypothetical Suppl. Estimand	Second Suppl. Estimand	Primary Estimand	Suppl. Estimand	
Initiation of rescue treatment	Observed	Treated as missing, MI	Treated as missing, MI	Value will be used as observed	NRI	Value will be used as observed	Not applicable
	Missing	MI	MI	MI	NRI	MI	Not applicable
Permanent discontinuation of IMP, for reasons other than lack of efficacy or an AE related to worsening of AD	Observed	Treated as missing, MI	Treated as missing, MI	Value will be used as observed	Treated as missing, MI	Value will be used as observed	Accounted for as a competing risk a
	Missing	MI	MI	MI	MI	MI	Accounted for as a competing risk a

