Permanent discontinuation of IMP, due to lack of efficacy or an AE related to worsening of AD	Observed	Treated as missing, LOCF	Treated as missing, MI	Value will be used as observed	NRI	Value will be used as observed	Accounted for as a competing risk a
	Missing	LOCF	MI	MI	NRI	MI	Accounted for as a competing risk a

THIS DOCUMENT CONTAINS CONFIDENTIAL INFORMATION AND MUST NOT BE COPIED OR MADE AVAILABLE TO ANY THIRD PARTY WITHOUT THE PRIOR WRITTEN CONSENT OF THE LEO PHARMA GROUP

Events	Observed data or missing	Continuous endpoints			Binary endpoints		TTE endpoints
		Primary Estimand	Hypothetical Suppl. Estimand	Second Suppl. Estimand	Primary Estimand	Suppl. Estimand	
No intercurrent events	Observed	Value will be used as observed	Value will be used as observed	Value will be used as observed	Value will be used as observed	Value will be used as observed	Not applicable
	Missing	MI	MI	MI	MI	MI	Not applicable

a) Withdrawal from trial will also be accounted for as a competing risk.

**Abbreviations:** AD = atopic dermatitis; AE = adverse event; IMP = investigational medicinal product; LOCF = last observation carried forward; MI = multiple imputation; NRI = non-responder imputation; Suppl. = supplementary; TTE = time-to-event.

THIS DOCUMENT CONTAINS CONFIDENTIAL INFORMATION AND MUST NOT BE COPIED OR MADE AVAILABLE TO ANY THIRD PARTY WITHOUT THE PRIOR WRITTEN CONSENT OF THE LEO PHARMA GROUP

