#### **11.3.7.3 Estimands for time-to-event endpoints**

The primary estimand for the time-to-event endpoint, time from baseline to the initiation of rescue treatment, quantifies the effect of treatment while subjects are receiving treatment.

The estimand is described by the following attributes:

- A. Target Population: Subjects with moderate-to-severe AD, as defined through the inclusion and exclusion criteria listed in Section 5.
- B. Variable: Time from baseline to the initiation of rescue treatment.
- C. Treatment conditions: LEO 138559 dose regimens 1-4 versus placebo.
- D. Strategies for handling intercurrent events:
  - a. Subjects permanently discontinuing IMP are considered to have experienced a competing risk, i.e. no longer considered at risk for initiating rescue treatment, in line with the while on treatment strategy.
- E. Population level summary: Difference in the cumulative incidence of initiation of rescue treatment at Week 16 between the treatment conditions.

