#### **11.3.8.3 Analysis of primary estimand for time-to-event endpoint**

##### **Primary analysis**

Let  $T$  represent the time from baseline to initiation of rescue treatment and  $T_{IE}$  represent the time from baseline to occurrence of permanent discontinuation of IMP or withdrawal from trial. The *while on treatment* estimand evaluates:

THIS DOCUMENT CONTAINS CONFIDENTIAL INFORMATION AND MUST NOT BE COPIED OR MADE AVAILABLE TO ANY THIRD PARTY WITHOUT THE PRIOR WRITTEN CONSENT OF THE LEO PHARMA GROUP

$$Pr(T < T_{IE} \wedge C_{admin})$$

where  $T_{IE} \wedge C_{admin}$  is the minimum of  $T_{IE}$  and the end of the treatment period (administrative censoring time), corresponding to Week 16. Since interest lies in estimating the time to initiating rescue treatment, the occurrence of permanent discontinuation of IMP or withdrawal from trial can be accounted for through the formulation of a competing risks model.

The null hypothesis,  $H_{0,i}: \lambda_{\text{LEO 138559, regimen } i}(t) = \lambda_{\text{placebo}}(t), \forall t \in (0,16)$ , where  $\lambda(t)$  denotes the sub-distribution hazard rate associated with the time-to-event endpoint at time  $t$  (measured in weeks) and  $i \in (1,2,3,4)$  denotes the LEO 138559 dose regimen, will be tested against the alternative,  $H_{A,i}: \lambda_{\text{LEO 138559, dosage regimen } i}(t) \neq \lambda_{\text{placebo}}(t)$  based on Gray's test, stratified by baseline disease severity (baseline vIGA-AD score), region (Japan, Other countries), and prior use of biologics or systemic JAK inhibitors for AD (Yes/No).

To quantify the magnitude of the potential treatment effect, the estimated cumulative incidence functions for the competing risks model will be presented for the treatment groups, based on the Aalen-Johansen estimator, along with 95% CIs.

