#### 11.3.9.4 Analysis of supplementary estimand for time to event endpoint

##### Primary analysis

Let  $T$  represent the time from baseline to the initiation of rescue treatment or permanent discontinuation of IMP, whichever occurs first. The *composite* estimand evaluates:

$$Pr(T < C_{admin})$$

where  $C_{admin}$  is the end of the treatment period (administrative censoring time), corresponding to Week 16.

The null hypothesis,  $H_{0,i}: \lambda_{\text{LEO 138559, regimen } i}(t) = \lambda_{\text{placebo}}(t), \forall t \in (0,16)$ , where  $\lambda(t)$  denotes the hazard rate associated with the time-to-event endpoint at time  $t$  (measured in weeks) and  $i \in (1,2,3,4)$  denotes the LEO 138559 dose regimen, will be tested against the alternative,  $H_{A,i}: \lambda_{\text{LEO 138559, dosage regimen } i}(t) \neq \lambda_{\text{placebo}}(t)$  based on the log-rank test, stratified by baseline disease severity (baseline vIGA-AD score), region (Japan, Other countries), and prior biologics or systemic JAK inhibitors for AD (Yes/No).

To quantify the magnitude of the potential treatment effect, the estimated cumulative incidence functions will be presented for the treatment groups, based on the Kaplan-Meier estimator, along with 95% CIs. Additionally, the difference in the estimated cumulative incidence functions at Week 16 between the LEO 138559 dose regimens and placebo will be presented along with 95% CIs.

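### The primary time-to-rescue analysis (11.3.8.3) does not plan the Week 16 difference in cumulative incidence that defines its estimand, and no rule covers a rescue that coincides with or triggers discontinuation

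*Combined protocol and SAP*

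**What the plan says.** Panel 3 lists time from baseline to any rescue treatment as an exploratory safety endpoint.

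**Estimand.** For its primary (while-on-treatment) estimand, Panel 4 gives the population-level summary as "Difference in the cumulative incidence at Week 16". Section 11.3.7.3, item E, gives it as "Difference in the cumulative incidence of initiation of rescue treatment at Week 16 between the treatment conditions".

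**Primary analysis, Section 11.3.8.3.** Each regimen is compared with placebo by a stratified Gray's test of sub-distribution hazards over Weeks 0 to 16. To show the size of the effect, "cumulative incidence functions for the competing risks model will be presented for the treatment groups, based on the Aalen-Johansen estimator, along with 95% CIs". The section stops there.

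**Supplementary analysis, Section 11.3.9.4.** For the composite of rescue or permanent discontinuation, the plan is a stratified log-rank test and Kaplan-Meier curves. It then adds that "the difference in the estimated cumulative incidence functions at Week 16 between the LEO 138559 dose regimens and placebo will be presented", with 95% CIs.

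**Event timing.** Section 11.3.8.3 defines a rescue event by T < T_IE (and before Week 16), where T_IE is the time of permanent discontinuation or trial withdrawal. Section 11.3.7 dates both events from the eCRF. For rescue: "The timing of the event will be taken as the date of initiation of the rescue treatment recorded in the eCRF". For discontinuation: "The timing of the event will be taken as the date of permanent discontinuation of IMP as recorded in the eCRF". Section 11.3.7.3 treats a subject who discontinues as "no longer considered at risk for initiating rescue treatment". Footnote a to Panel 16 adds: "Withdrawal from trial will also be accounted for as a competing risk".

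**Treatment rules.** Under Sections 4.1, 6.5 and 7.2.1, any rescue before Week 4 ends IMP permanently. So does rescue with anything other than TCS or TCI from Week 4 to the end of treatment.

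**The concern.** The estimand names one contrast and the analysis assigned to it does not produce that contrast. Gray's test does not fill the gap: it tests equality of sub-distribution hazards over the whole period and gives no estimate of the Week 16 difference. The supplementary estimand does get its contrast, in a section otherwise worded almost identically, so this looks like an omission and not a decision.

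The second matter is narrower. For some subjects the rescue is itself what ends treatment, and the two events may then share a date. Read literally, T < T_IE fails for them, so they become competing events on the ground that they can no longer start rescue, although they have just started it. They would be subjects with early intolerable disease, or with disease needing stronger rescue first, and the endpoint is meant to capture both.

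**Working it through.** **1. Estimand against analysis**

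| | Primary (while on treatment) | Supplementary (composite) |
|---|---|---|
| Summary in Panel 4 and 11.3.7.3 | Week 16 difference | Week 16 difference |
| Test | Gray, stratified | Log-rank, stratified |
| Curves per arm with 95% CI | Aalen-Johansen | Kaplan-Meier |
| Week 16 difference with 95% CI | not planned | planned (11.3.9.4) |

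**2. How precise the missing contrast would be**

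The plan gives no figure for this endpoint, so there is none to reproduce. The inputs are:
- 50 subjects per arm (Section 6.2).
- Planning rates for withdrawal or an intercurrent event by Week 16 of 40% on placebo and 20% on regimen 1 (Section 11.1).
- The rescue share of those rates, which is not given. I assume 25%, 50% or 75%, the same in both arms.

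Because withdrawal is a competing risk, nobody is censored before Week 16. The Aalen-Johansen estimate at Week 16 is therefore the number of rescues divided by 50. For placebo minus regimen 1:

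SE = sqrt(p0(1-p0)/50 + p1(1-p1)/50), 95% CI = (p0 - p1) ± 1.96 SE

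- 25% share: p0 = 10%, p1 = 5%. SE = sqrt(0.00180 + 0.00095) = 0.0524. Difference 5.0 points (-5.3 to 15.3).
- 50% share: p0 = 20%, p1 = 10%. SE = sqrt(0.00320 + 0.00180) = 0.0707. Difference 10.0 (-3.9 to 23.9).
- 75% share: p0 = 30%, p1 = 15%. SE = sqrt(0.00420 + 0.00255) = 0.0822. Difference 15.0 (-1.1 to 31.1).

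These are expected rates: 5% and 15% of 50 are not whole numbers of subjects.

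**3. Could a reader rebuild the interval from the per-arm CIs?**

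With l and u the per-arm limits, the rebuilt limits are:

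lower = d - sqrt((p0 - l0)² + (u1 - p1)²), upper = d + sqrt((u0 - p0)² + (p1 - l1)²)

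The CI type is not specified, so two common ones were tried:
- Log-log transform of the incidence: -5.6 to 15.8, -4.0 to 23.5 and -1.4 to 30.3. These limits lie within about 1 point of those in step 2.
- Log-log transform of one minus the incidence: at the 25% share, -7.6 to 17.9, which is 2.3 and 2.6 points away.

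Rebuilding works, but only approximately, and the result depends on an unstated choice.

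**4. Same-day rescue**

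If T = T_IE, then T < T_IE is false and the discontinuation stands as the competing event. Each such subject lowers that arm's Week 16 incidence by 1/50 = 2.0 points. The documents do not allow the number to be estimated.

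Replacing < by ≤ settles equal dates only. Section 7.2.1 has the date of the last dose recorded in the eCRF. If a date of that kind served as the discontinuation date, a rescue-triggered discontinuation would be dated before the rescue, and T ≤ T_IE would still fail.

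**The case against.** **On the contrast.** The measure, time point and comparator are fixed in 11.3.7.3 and the estimator in 11.3.8.3, so subtracting two planned estimates leaves no analytic choice open. This largely stands for the point estimate and is why the matter is minor. It does not supply the interval. A reader might also infer that the estimand itself requires a 95% CI. It does not: it names the difference, and the CI follows from the general rule in 11.3.1 and the parallel in 11.3.9.4.

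**On same-day rescue.** T < T_IE defines a population quantity and is not a coding instruction. The protocol describes rescue as leading to discontinuation, and the at-risk reasoning in 11.3.7.3 points to counting the rescue. That is fair, so the request is for a stated rule and not the correction of an explicit error.

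A reader might go further and conclude that the plan miscounts all early rescues. With exponential timing (11.1), 1 - 0.60^(4/16) = 12.0% of placebo and 1 - 0.80^(4/16) = 5.4% of regimen 1 subjects have an event before Week 4. If every event were a rescue and every early one tied, the difference would fall from 20.0 points (40% vs 20%; CI 2.5 to 37.5) to 13.4 (28.0% vs 14.6%; CI -2.4 to 29.3). The documents do not support this. The planning rates mix withdrawals with intercurrent events, and nothing says the dates will match. Nor does escalation after topical rescue from Week 4 create a tie, because T is already fixed at the topical start.

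**On the SAP.** Under 11.3.1 the SAP is finalised before unblinding and could settle both matters. No separate SAP text is among the documents reviewed. Unlike the imputation details, this contrast is not expressly deferred to it.

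**Conclusion.** The first part holds: as written, 11.3.8.3 does not estimate the contrast that defines its estimand. The consequence is a reporting gap. The endpoint is exploratory and outside the testing hierarchy of 11.3.6, so the primary endpoint, the error rate and the sample size are untouched. The intervals in the working rest on assumed rescue shares. They show that the contrast would be imprecise, not what it will be. At the three shares shown the interval includes 0, and at a 100% share it would not.

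The second part holds as an ambiguity. A literal reading moves a same-day rescue to the competing event at 2.0 points each, with unknown frequency. It can only lower an arm's rescue incidence, and its effect on the difference depends on which arm the cases fall in. Rescue that starts with TCS or TCI from Week 4 is unaffected, as is the composite analysis.

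**What to change.** In Section 11.3.8.3, or in the SAP before unblinding:

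1. Add the Aalen-Johansen Week 16 difference in cumulative incidence of rescue versus placebo, with 95% CI, for each regimen, matching 11.3.9.4. Name the CI method.
2. State that a rescue falling on the same date as permanent discontinuation, or triggering it, is counted as the rescue event whatever discontinuation date is recorded. Do not rely on T ≤ T_IE alone.

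The cost is two sentences and one further estimate per regimen. No new data and no change to the treatment rules are needed. Settling the second item before unblinding avoids a convention chosen with the results in view.

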### 11.3.9 Supplementary estimand analysis

#### 11.3.9.1 Analysis of hypothetical supplementary estimand for continuous endpoints

##### Primary analysis

Data collected after permanent discontinuation of IMP or after initiation of rescue treatment will be excluded from the analysis and “treated as missing”. Missing data and data “treated as missing” will be split into two groups:

1. Data “treated as missing” due to discontinuation due to lack of efficacy, an AE related to worsening of AD, or rescue treatment.
2. Missing data or data “treated as missing” for other reasons than discontinuation due to lack of efficacy, an AE related to worsening of AD, or rescue treatment.

The first group will have their missing values imputed using an ANCOVA model adjusting for treatment, region, and time as a continuous covariate. Noise will be added to the predicted values from the imputation model. The imputation will be repeated 100 times. Further details regarding the imputation model, including choice of seed, will be specified in the SAP.

The second group will be imputed using MI (100 iterations) under a MAR assumption within each treatment group. All subject-level data observed prior to the occurrence of an intercurrent event will be used to inform the imputation models. Further details regarding the specification of the imputation models will be specified in the SAP.

THIS DOCUMENT CONTAINS CONFIDENTIAL INFORMATION AND MUST NOT BE COPIED OR MADE AVAILABLE TO ANY THIRD PARTY WITHOUT THE PRIOR WRITTEN CONSENT OF THE LEO PHARMA GROUP

The imputed datasets will be combined to create 100 complete datasets. For each of the 100 complete datasets, the response will be analyzed using an ANCOVA model adjusted for treatment, baseline disease severity (baseline vIGA-AD score), region (Japan, Other countries), and prior use of biologics or systemic JAK inhibitors for AD (Yes/No). The model will also be adjusted for the baseline value of the dependent variable.

The pooled estimate of the difference in the LSmean change from baseline, along with the associated 95% CIs and nominal p-values will be presented. Inference will be based on applying Rubin's rules to the estimates and standard errors from the ANCOVA analysis of the imputed datasets.

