The LP0145-1486 trial was a phase 1 clinical trial conducted in 24 Japanese healthy volunteers with the aim of evaluating the PK and safety of single SC administration of LEO 138559 (█ mg, █ mg, or █ mg) or placebo. In this trial, the PK was as expected for the population. TMDD was observed at the lowest dose level (█ mg). As a result of █ dependency of the PK of LEO 138559, higher serum concentration was observed in Japanese subjects as compared to non-Japanese subjects due to a lower █ of Japanese subjects. However, Japanese subjects are expected to have the same exposure as non-Japanese subjects if the █ is the same, and the benefit/risk profile is thus not changed for Japanese subjects.

In a phase 2a trial (LP0145-1376), adults with moderate-to-severe AD were treated with LEO 138559 or placebo. A total of 58 subjects were randomized 1:1 into the 2 treatment groups, either LEO 138559 450 mg Q2W (with an additional LEO 138559 450 mg administration at Week 1) or placebo Q2W (with an additional placebo administration at Week 1), to evaluate the safety and efficacy over a treatment period of 16 weeks, followed by a 16-week follow-up period. The primary endpoint was change from baseline in EASI score at Week 16. The secondary endpoint was the number of TEAEs from baseline to Week 16. In this phase 2a trial, the primary endpoint was met, with a statistically significant improvement in EASI score at Week 16 in the LEO 138559 450 mg Q2W group versus placebo. Fewer subjects in the LEO 138559 group (7 subjects) than in the placebo group (11 subjects) discontinued IMP and/or withdrew from the trial. The most frequent reasons for IMP discontinuation were: AEs in the LEO 138559 group (6 subjects, of which 4 had AEs related to COVID-19 infection) and withdrawal by subject in the placebo group (7 subjects). Note that as per protocol, subjects that were positive for SARS-CoV-2 (COVID-19) had to permanently discontinue IMP. No SAEs and no AE patterns giving rise to any concerns were reported.

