## 11 Statistical considerations

### 11.1 Sample size

A total of 250 subjects, including at least 25 Japanese subjects will be randomized in a 1:1:1:1:1 ratio to 1 of the 5 treatment regimens outlined in Section 6.2.

The sample size is chosen, based on the results of a simulation. The simulation assessed the power to reject the null hypotheses included in the testing hierarchy specified in Section 11.3.6. Additionally, the simulation was used to discern, for which effect sizes, the trial would have approximately 50% power to detect a significant difference, in the mean percent change from baseline in EASI score at Week 16 between dose regimens 1 and 2, at the 5% significance level.

The percent change from baseline was simulated in a 4-step process. First, baseline EASI scores were obtained by resampling from a large phase 3 development program in moderate-to-severe AD. Next, the change from baseline was simulated for each subject under a multivariate normal assumption. The assumed mean change from baseline in EASI score from Week 1 to 16 was based on a component related to the effect of treatment, provided in Panel 14 for all 5 dose regimens and an effect related to the baseline EASI score for each assessment.

#### Panel 14: Assumed values for the mean change from baseline in EASI score from Week 1 to Week 16

	Wk 1	Wk 2	Wk 3	Wk 4	Wk 6	Wk 8	Wk 10	Wk 12	Wk 14	Wk 16
Dose regimen 1	-6.8	-10.3	-13.8	-17.3	-19.6	-18.8	-18.2	-17.8	-19.3	-20.7
Dose regimen 2	-5.0	-7.6	-10.2	-12.8	-14.5	-13.9	-13.5	-13.2	-14.3	-15.3
Dose regimen 3	-5.0	-6.8	-9.2	-11.5	-13.1	-12.5	-12.2	-11.9	-12.9	-13.8
Dose regimen 4	-3.3	-5.0	-6.6	-8.3	-9.4	-9.0	-8.8	-8.6	-9.3	-10.0
Placebo	-1.9	-3.8	-4.2	-4.6	-5.4	-3.8	-4.6	-5.4	-4.5	-3.5

Abbreviations: Wk = Week.

The assumptions for the placebo and dose regimen 2 groups are based on the observed data from the phase 2a proof-of-concept trial. Based on PK/PD modeling, it is anticipated that dose regimens 3 and 4 will retain approximately 90% and 65% of the mean change from baseline in EASI score observed for dose regimen █ in the phase █ trial. For dose regimen 1, the mean change from baseline in EASI score from Week 1 to Week 16 is assumed to have an additional reduction of 35% compared to dose regimen 2.

THIS DOCUMENT CONTAINS CONFIDENTIAL INFORMATION AND MUST NOT BE COPIED OR MADE AVAILABLE TO ANY THIRD PARTY WITHOUT THE PRIOR WRITTEN CONSENT OF THE LEO PHARMA GROUP

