The covariance matrices for the 5 dose regimens in the simulation were assumed to be equal and have a compound symmetry structure with variances equal to 111.0 and covariances equal to 32.5.

The third step was to ensure that the underlying EASI scores from Week 1 to 16 were within the range of the EASI score scale, which runs from [0,72]. This implies natural bounds for the individual simulated changes from baseline in EASI score, as they must lie within the interval, [-baseline score, 72-baseline score].

The final step was to derive the percent change from baseline in EASI score from Week 1 to Week 16, by dividing the simulated changes in baseline in EASI score from Week 1 to 16 by the subject's baseline EASI score.

The simulation further assumed that percentage of subjects withdrawing or experiencing an intercurrent event by Week 16 in dose regimens 1-4 and placebo arms are 20%, 20%, 30%, 40%, and 40%, respectively, the timing of which was assumed to be exponentially distributed.

To approximate the power, 1,000 data sets with 250 subjects were generated based on the randomization scheme. For each data set, 100 complete versions were generated by imputing missing data separately for each treatment arm. The baseline and all post-baseline EASI assessments were included in the imputation model. The imputed data sets were analyzed based on an ANCOVA model. The pooled estimate of the difference in the LSmean change from baseline, along with the associated 95% Cis and nominal p-values, were derived for each simulated data set by applying Rubin's rules to the estimates and standard errors from the ANCOVA analysis of the imputed datasets.

**Panel 15** provides the nominal power as well as the prioritized power based on the hierarchical testing procedure, to reject the null hypotheses testing the LEO 138559 dose regimens 1-4 versus placebo, with respect to the differences in the mean percent change in EASI score from baseline to Week 16.

THIS DOCUMENT CONTAINS CONFIDENTIAL INFORMATION AND MUST NOT BE COPIED OR MADE AVAILABLE TO ANY THIRD PARTY WITHOUT THE PRIOR WRITTEN CONSENT OF THE LEO PHARMA GROUP

**Panel 15: Approximate nominal and prioritized power for rejecting the null hypotheses including in the testing hierarchy, based on the results of the simulation**

Hypothesis	Nominal power	Prioritized power
Dose regimen 1 vs Placebo	~100%	~100%
Dose regimen 2 vs Placebo	99.1%	~99.1%
Dose regimen 3 vs Placebo	97.2%	~96.4%

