### 11.3.6 Testing strategy

The following hierarchical procedure will be used to ensure strong control of the familywise error rate at the 5% significance level (two-sided significance tests), when testing the null hypotheses associated with the primary endpoint, percent change in EASI score from baseline to Week 16:

1. LEO 138559 [REDACTED] mg SC Weeks 0, 1, 2, 3 and then [REDACTED] mg Q2W from Week 4 (dose regimen 1) versus placebo.
2. LEO 138559 [REDACTED] mg SC Weeks 0, 1, 2 and then [REDACTED] mg Q2W from Week 4 (dose regimen 2) versus placebo.
3. LEO 138559 [REDACTED] mg SC Weeks 0 and 2 and then [REDACTED] mg Q2W from Week 4 (dose regimen 3) versus placebo.
4. LEO 138559 [REDACTED] mg SC Weeks 0 and 2 and then [REDACTED] mg Q2W from Week 4 (dose regimen 4) versus placebo.

Under the hierarchical procedure, the first null hypothesis (the difference in the mean percent change in EASI score from baseline to Week 16 between dose regimen 1 and placebo is equal to 0), is tested at the 5% significance level. If that null hypothesis is rejected, the procedure will proceed to test null hypothesis 2 at the 5% significance level. However, if the first null hypothesis cannot be rejected, the procedure stops and null hypotheses 2-4 will not be formally tested. The procedure continues in this fashion, until it either encounters a null hypothesis that cannot be rejected, or all null hypotheses have been rejected. For the purposes of the hierarchical testing procedure, the hypothesis tests will be based on the analysis of the primary estimand for the primary endpoint.

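### The group 1 imputation model in Section 11.3.9.1 forces one time slope on all arms and omits baseline; under the Panel 14 means this modestly shrinks the hypothetical supplementary effects

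*Combined protocol and SAP*

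**What the plan says.** Section 11.3.9.1 removes data after permanent discontinuation of IMP or rescue and splits the missing values in two. Group 1 covers rescue, lack of efficacy and AEs of worsening AD; group 2 is everything else. Group 2 is imputed by MI separately within each arm. For group 1: "The first group will have their missing values imputed using an ANCOVA model adjusting for treatment, region, and time as a continuous covariate". Then: "Noise will be added to the predicted values from the imputation model". The step is repeated 100 times, and "Further details regarding the imputation model, including choice of seed, will be specified in the SAP". The completed data are analysed by an ANCOVA that does adjust for the baseline value, and results are pooled by Rubin's rules. Panel 16 labels the handling of these subjects as MI.

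Section 11.1 gives the planning means (Panel 14). Two rows are empirical: "The assumptions for the placebo and dose regimen 2 groups are based on the observed data from the phase 2a proof-of-concept trial". The others are scaled from regimen 2; for example, regimen 1 "is assumed to have an additional reduction of 35% compared to dose regimen 2". The assumed proportions with withdrawal or an intercurrent event by Week 16 are 20%, 20%, 30% and 40% for regimens 1-4 and 40% for placebo, with no split into groups 1 and 2.

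Section 11.3.6 settles what is formally tested: "the hypothesis tests will be based on the analysis of the primary estimand for the primary endpoint".

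**The concern.** A model with main effects of treatment and time gives every arm the same weekly change, so its treatment difference is constant over visits. Panel 14 assumes the opposite: the gap to placebo widens from -4.9 at Week 1 to -17.2 at Week 16 for regimen 1, and from -1.4 to -6.5 for regimen 4. Week 16 values imputed from a visit-averaged difference will then be too close together, and the supplementary effect moves toward zero. This analysis uses the same hypothetical strategy as the primary one and was added as a robustness check, so a difference between the two would be read as sensitivity to the primary imputation. Part of that difference could come from the missing interaction.

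**Working it through.** Inputs from Section 11.1: Panel 14 means, variance 111.0, covariance 32.5, 50 subjects per arm, and the event rates above. Not in the documents: the share f of events in group 1, the baseline EASI distribution, the fitting data and the response scale.

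1. Reproduce the plan's power. Completers are 50 x (1 - event rate) = 40, 40, 35, 30, and 30 on placebo. z = gap / sqrt(111.0 x (1/n_active + 1/n_placebo)); power = Phi(z - 1.96). Regimen 4: 6.5 / sqrt(111.0 x 2/30) = 6.5/2.72 = 2.39, power 66.6% (Panel 15: 67.4%). Regimens 1-3: about 100%, 99.6%, 97.6% (Panel 15: about 100%, 99.1%, 97.2%). Regimen 1 vs 2 comes out at 63.0% against 49.7%, because this shortcut ignores the -100% floor. A percent-change simulation with the stated bounds and an assumed baseline (mean 32, SD 13), analysing completers only, gives 49.2%.

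2. Slopes. Least squares on week within each Panel 14 row gives -0.67, -0.50, -0.44, -0.33 per week for regimens 1-4 and -0.07 for placebo. With equal visit weights the common slope is their average, -0.401.

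3. Week 16 prediction. The mean visit week is 7.6, so the prediction is the arm's mean over visits - 0.401 x (16 - 7.6), that is, the mean - 3.37.

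| Arm | Mean over visits | Model, Week 16 | Panel 14, Week 16 | Error b | Model gap | Panel 14 gap | Kept |
|---|---|---|---|---|---|---|---|
| 1 | -16.26 | -19.63 | -20.7 | +1.07 | -12.09 | -17.2 | 70% |
| 2 | -12.03 | -15.40 | -15.3 | -0.10 | -7.86 | -11.8 | 67% |
| 3 | -10.89 | -14.26 | -13.8 | -0.46 | -6.72 | -10.3 | 65% |
| 4 | -7.83 | -11.20 | -10.0 | -1.20 | -3.66 | -6.5 | 56% |
| Placebo | -4.17 | -7.54 | -3.5 | -4.04 | | | |

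The two phase 2a rows alone give a slope of -0.283, placebo at -6.55, and the same 67% for regimen 2.

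4. Trial-level shift = f x (e_active x b_active - e_placebo x b_placebo), where e is the event rate. Regimen 1, f = 1: 0.20 x 1.07 + 0.40 x 4.04 = 1.83, or 10.6% of 17.2. Regimen 4: -0.40 x 1.20 + 0.40 x 4.04 = 1.14, or 17.5% of 6.5. For regimens 1-4: 2.7/3.4/3.6/4.4% at f = 0.25; 5.3/6.8/7.2/8.7% at 0.5; 10.6/13.5/14.3/17.5% at 1.

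5. Simulation on percent change (2,000 trials, 20 imputations; assumed baseline mean 34.7, SD 10.8, baseline slope -0.3, no region effect, imputation on EASI change, fit to all pre-event data, events independent of outcome): 3.3/4.3/4.4/5.8%, 6.4/8.4/8.5/10.5% and 12.8/16.7/17.0/19.9% at the same three shares. At a quarter to a half this is 1.1-3.2 percentage points, against a sampling SD of 7-8. Doubling the group 1 hazard per 10 EASI points gives similar sizes. In phase 2a at most 3 of 7 active and 4 of 11 placebo discontinuations could have been group 1 (rescue use not reported); those shares give 4.7/6.0/5.8/7.0%.

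6. Reversed event rates (40% active, 20% placebo, half group 1): the simulation gives 2.9/2.7/1.2/1.4%. The step 4 formula gives 0.5 x (0.40 x 1.07 + 0.20 x 4.04) = 0.62, or 3.6%, for regimen 1, and 0.5 x (-0.40 x 1.20 + 0.20 x 4.04) = 0.16, or 2.5%, for regimen 4.

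7. With arm-specific slopes the fitted gaps keep 100/98/96/90%. With the full fix the simulated shrinkage is 0.5-2.0%, 0.8-2.9% and 1.5-4.7% at the three shares, or up to 7.9% if all events are group 1 and failure follows poor response.

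8. Other benchmark: group 1 stays at its last value. For regimen 4 at half share, the listed model is off by about +1% and the fixed model overstates by about 8-9% (about 20% if all events are group 1). For regimens 1-3 the listed model is off by -3 to -8% and the fixed model by -3 to +4%.

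**The case against.** The strongest counter-argument is the benchmark in step 8. If failures would have stayed where they were, the listed model is nearly right for regimen 4 and the fix is not. That stands as arithmetic. But it is the assumption behind LOCF in the primary analysis. The supplementary analysis, labelled MI, targets outcomes under continued treatment, and on that benchmark the fix has less bias for all four regimens.

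Two stronger readings are tempting. A reader might infer that imputing improvement for placebo failures contradicts the expectation in Section 11.3.8.1 that such subjects would not improve. The documents do not support this: that expectation justifies LOCF, covers failures on active as well as placebo, and cannot be combined with a Panel 14 benchmark. A reader might also infer that regimen 4 is most at risk. It has the largest percentage shrinkage, but its RMSE at half share is the same with and without the fix, and under LOCF the ranking of the two models reverses.

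The deferral to the SAP is a partial answer. It covers further details, including possibly parameter draws, since the kind of noise is not specified; it does not withdraw the covariate list already stated. It is also fair that shrinkage toward zero is tolerable in a robustness analysis.

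**Conclusion.** The point holds as a cheap improvement to a supplementary estimand. The primary analysis, the testing hierarchy and the Panel 15 power are untouched, and a positive supplementary result would still support robustness. The shrinkage is roughly 3-6%, 5-10% or 11-20% (upper bound) with a quarter, half or all of events in group 1, and about 1-3% if events are commoner on active. These sizes assume that group 1 subjects would have followed their arm's Panel 14 means, and rest on an assumed group 1 share and baseline distribution. The non-parallel shape itself rests on two phase 2a rows from a 58-subject trial; the other rows are scaled copies of regimen 2. The fixed analysis and LOCF should be read as two different assumptions about failures, not as one checking the other's arithmetic. For that comparison, Panel 16 (MI after rescue in the primary estimand) and Section 11.3.8.1 (LOCF after rescue) need to be reconciled.

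**What to change.** In Section 11.3.9.1 and the SAP, add a treatment-by-time interaction and the baseline value to the group 1 imputation model. State the response scale and that the model is fitted to the pre-event data of all subjects. Draw the model parameters as well as noise, so that Rubin's rules apply.

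The cost is a few words and slightly more variance. At half share the regimen 4 SD goes from 7.8 to 8.0 points, and RMSE for regimens 1-4 goes from 7.7/7.9/8.0/8.1 to 7.2/7.5/7.8/8.1. These figures are for the whole package, not the interaction alone. The fix should not be used if the model is fitted to group 1 subjects only: RMSE is then worse, 9.0-9.5 against 7.8-8.4. Some bias remains because time stays linear. Treatment-by-visit terms or within-arm MI remove more of it but cost more variance: with all events in group 1 the regimen 4 SD is 8.7 or 9.0, against 7.3 for the fix.
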